4.0 Abbreviations and Definitions

AUC	area under the serum plasma concentration-time curve
AUC_(0-tlast)	area under the serum plasma concentration-time curve from time zero to last measurable plasma concentration
AUC_(0-∞)	area under the serum plasma concentration-time curve from time zero to infinity
AUC_{0-T}	area under the serum versus time concentration-time curve over the dosing interval
C_{av,T}	average serum concentration over the dosing interval
C_{max}	maximum serum plasma concentration
C_{min,T}	minimum serum concentration over the dosing interval
EC₅₀	the half maximal effective serum concentration
Q2W	once every 2 weeks

5.2.1 Primary Objective

The primary objective of this study is to determine an RP2D and schedule of LY3164530 that may be safely administered to patients with advanced or metastatic cancer.

5.3.1 Mechanism of Action and In Vitro/In Vivo Activity

LY3164530 has high affinity for both MET and EGFR and binds both receptors simultaneously in tumor cells. As described in the Investigator's Brochure (Section 5.2.2), binding of LY3164530 to MET and EGFR blocks activation of both receptors by their respective ligands. In addition to its ligand-blocking activity, LY3164530 also leads to internalization and degradation of both receptors in tumor cells. The ability of LY3164530 to internalize both receptors is superior to the combination of ~~the 2 component~~ individual monoclonal antibodies. The internalization of both receptors is most commonly observed in cells expressing high levels of MET. In addition, LY3164530 also increases the avidity binding to MET in cells expressing both MET and EGFR, leading to better neutralization of HGF compared to the parental MET antibody alone or in combination with cetuximab. The ability of LY3164530 to block ligand-receptor interactions and efficiently internalize MET and EGFR, and its increased avidity for MET, is believed to be responsible for the in vitro antiproliferative activity observed against a panel of tumor cell lines. In vivo, administration of LY3164530 results in dose-dependent antitumor activity in cell line-derived non-small cell lung cancer, gastric cancer, and squamous

cell cancer of the head and neck (SCCHN) xenografts, as well as in colorectal cancer and SCCHN patient-derived xenografts.

An interim analysis of the LY3164530 PK data was conducted from all of the 15 patients who received at least 1 dose of LY3164530 administered as a 1 or 2-hour infusion once every 2 weeks (Q2W) across the dose range of 300-1250 mg. Dose-dependent increases in the systemic exposure (AUC, C_{max}) of LY3164530 following single and multiple doses were observed. A minor amount of accumulation in serum was observed within Cycle 1 and between Cycles 1 and 2 of treatment after 1000 mg Q2W (mean accumulation ratio of 1.1 within and between cycles). The LY3164530 systemic clearance (CL) decreased by approximately 2-fold on average when the dose was escalated from 600 mg to 1000 mg, indicating the saturation of cell-surface receptors by LY3164530 and a slower non-receptor-mediated clearance predominating at doses >600 mg. While a more rapid receptor-mediated clearance (ie, target mediated drug disposition [TMDD]) predominates at low doses (ie, ≤600 mg). In addition, the LY3164530 exposure following 1000 mg Q2W appears to be in an exposure range expected to achieve biological effects based on the nonclinical MKN45 xenograft PK/PD model estimates for the MET and EGFR half maximal effective serum concentrations (EC_{50}) values. The LY3164530 maximum serum concentration (C_{max}) after 1000 mg in Cycles 1 and 2 is greater (mean C_{max} range: 295-394 µg/mL) than both the MET EC_{50} (79.5 µg/mL; 0.4 µM) and EGFR EC_{50} (7.95 µg/mL; 0.04 µM) concentrations. The average LY3164530 serum concentration over the dosing interval ($C_{av,\tau}$) during Cycles 1 and 2 is also greater (mean $C_{av,\tau}$ range: 102-132 µg/mL) than the MET EC_{50} and EGFR EC_{50} . However, the minimum serum concentration over the dosing interval ($C_{min,\tau}$) of LY3164530 following 1000 mg in Cycles 1 and 2 (mean $C_{min,\tau}$ range: 19-49 µg/mL) is lower

than the MET EC_{50} (79.5 ug/mL), which is the desired concentration to maintain throughout the dosing interval in order to maximize the biological activity of LY3164530.

At a dose of 1000 mg, the mean terminal elimination-life ($t_{1/2}$) is approximately 100 hours (approximately 4 days). As a result, the administration of LY3164530 every 2 weeks may not be the optimal schedule of administration in order to achieve a LY3164530 $C_{min,\tau}$ near the MET EC_{50} . Therefore, it is hypothesized that weekly dosing of LY3164530 (ie, Days 1, 8, 15, and 22 of a 28 day cycle) will minimize the fluctuation between the peak (C_{max}) and trough ($C_{min,\tau}$) serum concentrations of LY3164530 leading to a more consistent inhibition of both MET and EGFR over the dosing interval (with minimal impact on the accumulation of LY3164530) and potentially greater pharmacologic activity (PD response). The MTD of LY3164530 when administered on Days 1 and 15 of a 28 day cycle is 1000 mg. As a result, the starting dose for the weekly schedule will be 500 mg. The safety, toxicity, PK, and PD associated with a weekly schedule will be assessed.

6.2 Summary of Study Design

Study JNBA is a multicenter, nonrandomized, open label, dose escalation Phase 1 study of IV LY3164530 in patients with advanced and/or metastatic cancer. Eligible patients will receive LY3164530 as an infusion on Days 1 and 15 (Schedule 1) or on Days 1, 8, 15, and 22 (Schedule 2) of each cycle. A cycle will consist of 28 days and the schedules will enroll in parallel.

Dose escalation will be driven by a modified toxicity probability interval (mTPI) method. The RP2D and schedule will be determined once at least 10 patients, but no more than 20, are treated at a dose and schedule that is at or below the maximum tolerated dose (MTD). The actual sample size for Study JNBA is anticipated to be approximately 50 patients dependings on the incidence of DLTs and is anticipated to be approximately 50 patients.

...

7.2.1 Dosing Schedule

For doses less than ≤ 1000 mg, LY3164530 will be administered intravenously over approximately 60 minutes, on Days 1 and 15 of each 28-day cycle. The Sponsor may instruct sites to extend the infusion time for up to 3 hours for doses ≥ 1000 mg.

LY3164530 will be administered on Days 1 and 15 every 28 days (Schedule 1) or on Days 1, 8, 15, and 22 every 28 days (Schedule 2). The assigned dose, schedule, and duration of infusion of

LY3164530 will be provided by the Sponsor on a patient registration form. A patient will be assigned to either Schedule 1 or Schedule 2 and will be maintained on that schedule for the duration of therapy. Subsequent doses and/or infusion times should be adjusted as described in Section 7.2.5.

7.2.2.3 Dose Escalation Method

...

		Number of patients treated at current dose																			
		1	2	3	4	5	6	7	8	9	10	11	12	13	14	15	16	17	18	19	20
Number of DLTs	0	E	E	E	E	E	E	E	E	E	E	E	E	E	E	E	E	E	E	E	E
	1	D	S	S	S	S	E	E	E	E	E	E	E	E	E	E	E	E	E	E	E
	2		DU	D	S	S	S	S	S	S	S	E	E	E	E	E	E	E	E	E	E
	3			DU	DU	D	S	S	S	S	S	S	S	S	S	S	E	E	E	E	E
	4				DU	DU	DU	D	D	S	S	S	S	S	S	S	S	S	S	S	S
	5					DU	DU	DU	DU	DU	D	S	S	S	S	S	S	S	S	S	S
	6						DU	DU	DU	DU	DU	DU	D	S	S	S	S	S	S	S	S
	7							DU	D	D	S	S	S	S	S						
	8								DU	D	S	S	S								
	9									DU											
	10										DU										
	11											DU									
	12												DU								
	13													DU							
	14														DU						
	15															DU	DU	DU	DU	DU	DU
	16																DU	DU	DU	DU	DU
	17																	DU	DU	DU	DU
	18																		DU	DU	DU
	19																			DU	DU
	20																				DU

E = Escalate to the next higher dose
 S = Stay at the current dose
 D = De-escalate to the next lower dose
 U = The current dose is unacceptably toxic
 MTD = 30%
 Equivalence Interval = (28.7%, 30.1%)

Figure JNBA.1. Dose-finding spreadsheet of the modified toxicity probability interval method showing number of patients treated at a given dose vs. number of DLTs observed at that dose .

The beginning dose level for Schedule 1 ~~will be~~ 300 mg. The starting dose level for Schedule 2 will be 500 mg. The dose will be escalated by a maximum increment of 100%. If the beginning dose level is determined to be unacceptably toxic, a -1 dose level may be explored.

The exact increment will be determined by the investigators and Lilly CRP/CRS, and may be less than the maximum increment allowed in the protocol. Safety data will be the primary criteria for both the decision to dose-escalate and for selecting the dose to be administered in the next cohort. In addition, if available at the time of the dose escalation decision, PK (maximum plasma serum concentration [C_{max}], area under the plasma serum concentration-time curve [AUC], and CL) and/or PD results will be used as secondary/supporting data for dose escalation. No dose escalation can occur without prior discussion and agreement between the investigator

and the Lilly CRP or CRS; the decision will be documented in writing. Inpatient dose escalations are not permitted.

Although an example escalation table is shown in Table JNBA.3, alternate doses may be selected.

Table JNBA.3. Sample Dose Escalation Schema

Dose Level (Cohort)	Schedule 1 Dose	Schedule 2 Dose
-1	100 mg	400 mg
1	300 mg	500 mg
2	600 mg	600 mg
3	1000 mg	700 mg
4	1400 -1250 mg	
5	1700 mg	
6	2000 mg	

In Cohort 1 for Schedule 1 only, the first patient is required to complete a full cycle (28 days) before subsequent patients can be dosed. Subsequent patients in Cohort 1 can be dosed concurrently. Beginning with Cohort 2 for Schedule 1; and for all cohorts with Schedule 2, patients within a cohort can be dosed concurrently.

...

7.2.4.1 Infusion-Related Reactions

Due to the risk of hypersensitivity reactions with any biological agents, all patients should continue to be closely monitored for signs and symptoms indicative of an infusion-related reaction both in the acute period (immediately or within 24 hours after dosing) and up to several days to a few weeks after dosing for delayed reactions. In Cycles 1 and 2, Aacute assessments should include an assessment of vital signs starting at the time of initiation of the infusion and continuing until at least 60 minutes after the end of the infusion. At a minimum, vital signs should be obtained prior to infusion, during infusion, and at 1 hour post-infusion. The exact frequency of the monitoring is left to the discretion of the investigator. Monitoring should be performed in an area where resuscitation equipment and other agents (eg, epinephrine, corticosteroids) are readily available.

...

7.2.4.2 Skin Rash Reactions

Skin rash is a known toxicity of EGFR inhibitors, and skin effects were observed with LY3164530 in a 5-week repeat-dose toxicity study in monkeys. In Study JNBA, skin reactions were observed at all dose levels with Schedule 1 and were dose limiting at 1250 mg. As a result, Prophylaxis is not permitted for the initial dose of LY3164530. ~~so that the toxicities of LY3164530 may be appropriately characterized. However, i~~Institutional-approved standard of

care premedication for EGFR inhibitors, such as dexamethasone and/or topical and/or oral antibiotics, may be administered for the initial and subsequent doses.

~~If skin rash is identified as a DLT, prophylaxis may be permitted for the Cycle 1 Day 1 dose. Since LY3164530 is a bispecific antibody with a fixed stoichiometry for EGFR/MET, in the case of skin rash only DLT, prophylaxis may be explored to maximize the chances of effective combined MET/EGFR. This decision will be made following discussions with the investigators and the Lilly CRP/CRS and will be documented in writing. The dose escalation rules in Figure JNBA.1 would be followed if this change is implemented.~~

...

7.2.5.1 Dose Delays and Omissions

The following rules should guide dosing:

- Before each ~~dose~~ cycle of LY3164530 the following parameters are required:
 - Hematologic: ANC $\geq 1.5 \times 10^9/L$, platelets $\geq 75 \times 10^9/L$, and hemoglobin ≥ 8 g/dL.
 - Non-hematologic: AEs must resolve to CTCAE v 4.03 Grade ≤ 1 , or baseline. Exceptions will be made for: alopecia, fatigue, skin reactions, or other toxicities that can be controlled with standard treatment; these toxicities must resolve to \leq Grade 2.
- The start of a cycle is the date of the Day 1 dose.
 - For Schedule 1: If the Day 15 dose cannot be administered within 21 days of the prior dose (by Day 22), it should be omitted. The interval between LY3164530 doses must not be less than 14 days. If a dose is delayed (for toxicity or other circumstances), the next dose should be adjusted so that there is at least a 14-day interval.
 - For Schedule 2: If a dose cannot be administered within 10 days of the prior dose, it should be omitted. The interval between LY3164530 doses must not be less than 7 days. If a dose is delayed (for toxicity or other circumstances), the next dose should be adjusted so that there is at least a 7-day interval.
 - ~~The interval between LY3164530 doses must not be less than 14 days. If a dose is delayed (for toxicity or other circumstances), the next dose should be adjusted so that there is at least a 14-day interval.~~

If a dose cannot be administered within 28 days of the prior dose due to an AE, the patient should be removed from study drug treatment and should complete subsequent follow-up (Table JNBA.4).

- If the patient has completed the initial on-study radiographic assessment (eg, at the end of Cycle 2) is in Cycle 3 or beyond and is continuing to receive benefit from therapy, delays of greater than 28 days may be acceptable if agreed upon by both the investigator and Sponsor. For instance, if a patient has a non-drug-related AE such as prolonged flu, the patient may

continue on therapy if, in the opinion of the investigator, he/she is showing benefit from therapy and has recovered sufficiently from the AE.

- A delay of no more than 7 days because of holidays, weekends, inclement weather, or other justifiable events will be permitted and will not be counted as a protocol deviation.

7.2.5.2 Dose Adjustments

Dose adjustments should follow the guidance in Table JNBA.4.

For patients requiring dose reductions, reescalation to the original assigned LY3164530 dose is not allowed. The patient must be maintained at a reduced dose level for all remaining cycles.

Table JNBA.4. Dose Modifications and Treatment Alterations in Patients Treated with LY3164530

Toxicity	CTCAE_Grade	Recommendations
Infusion-related Reaction	Grade 1 First occurrence	Decrease the LY3164530 infusion rate by 50% and monitor closely for any worsening. For subsequent infusions, premedicate with diphenhydramine hydrochloride; additional premedication may be administered at the investigator's discretion.
	Grade 2 First occurrence	Stop LY3164530 infusion. Administer diphenhydramine hydrochloride and acetaminophen for fever and oxygen. Resume infusion at 50% of previous rate once infusion-related reaction has resolved or decreased to Grade 1 in severity, and monitor closely for any worsening. For subsequent infusions, premedicate with diphenhydramine hydrochloride; additional premedication may be administered at the investigator's discretion. The reduced rate should be used for all subsequent infusions.
	Grade 1 or 2 Second occurrence	Administer dexamethasone. For subsequent infusions, premedicate with diphenhydramine hydrochloride, acetaminophen, and dexamethasone. The reduced infusion rate should be used for all subsequent infusions.
	≥Grade 3	Stop LY3164530 infusion immediately and disconnect infusion tubing from the patient. Administer diphenhydramine hydrochloride, dexamethasone, bronchodilators for bronchospasm, and other medications/treatment as medically indicated. Patients must not receive any further LY3164530 treatment.
Skin reactions (eg, acne-like rash)	Grade 3 First occurrence	Delay or omit LY3164530 treatment until ≤Grade 1 following the rules in Section 7.2.5.1. Treatment with topical and/or oral antibiotics may should be considered.
	Grade 3 Second occurrence	Delay or omit LY3164530 treatment until ≤Grade 1 following the rules in Section 7.2.5.1. Dose reduce by 20% from assigned dose to the dose level used for the previous cohort for second occurrence. Treatment with topical and/or oral antibiotics may should be considered.
	Grade 3 Third occurrence Or Grade 4	Patients must not receive any further LY3164530 treatment.
Other toxicities	≥Grade 3 First occurrence	Delay or omit LY3164530 treatment until ≤Grade 1 or baseline following the rules in Section 7.2.5.1. Based on the investigator's discretion, the full dose of LY3164530 may be administered or the dose may be reduced to the next lowest dose level. If event recurs at same grade, then dose reduce LY3164530 to the next lowest dose.
	≥Grade 3 Second occurrence	Delay or omit LY3164530 treatment until ≤Grade 1 or baseline following the rules in Section 7.2.5.1. If event recurs at same grade, then dose reduce LY3164530 to the next lowest dose. Exceptions may be made for transient changes in electrolytes that respond to treatment.

Abbreviation: CTCAE = Common Terminology Criteria for Adverse Events.

Note: In addition, the dose may be reduced to the next lowest level for any toxicity at the discretion of the investigator.

7.3 Method of Assignment to Treatment

Patients who meet all criteria for enrollment will be assigned to receive LY3164530 in this study. Before each patient's enrollment into the study, an eligibility check must be conducted between the investigational site and the Lilly clinical research personnel to confirm that each patient meets all enrollment criteria. Upon confirmation of eligibility, the Sponsor will confirm the dose, schedule, infusion duration, and identification number assignment for each patient.

7.5 Concomitant Therapy

...

Patients should receive full supportive care during the trial. Routine prophylactic use of granulocyte colony-stimulating factors (G-CSF) is not permitted during this study. Should the use of hematopoietic colony-stimulating factors (CSFs) be necessary, follow the American Society of Clinical Oncology (ASCO) recommendations for the use of CSFs (Smith et al. 2006 2015).

...

8.1 Safety Evaluations

The safety and tolerability of LY3164530 have been assessed in nonclinical toxicology studies and this ongoing Phase 1 study. ~~and~~ The results from these studies are detailed in the Investigator's Brochure. This Phase 1 study contains safety monitoring that will permit initial characterization of the safety profile of LY3164530 in patients with advanced or metastatic cancer. Study procedures and their timing, including collection of patient samples, are described in the Study Schedule (Attachment 1).

...

8.2.2.2. Pharmacodynamic Samples

At the visits and times specified in Attachment 3, serum and plasma samples will be collected. The effect of LY3164530 on MET and EGFR pathway-specific targets may be explored to determine changes in potential biomarkers such as circulating levels of the MET ligand HGF, EGFR ligands (eg, EGF, TGFalpha), MET/ECD, and EGFR/ECD. These samples may be used for exploratory research on new biomarkers related to the MET/HGF and EGFR pathway. In addition, exploratory samples to assess proteomic panel may be collected. A maximum of 3 timepoints may be removed per dosing schedule during the study if warranted and agreed upon between both the investigator and Lilly.

...

8.2.3.3 Exploratory Biomarker Blood Samples

...

8.3 Efficacy Evaluations

A secondary objective of the study is to document any antitumor activity. Refer to Attachment 1 for details regarding the timing of specific efficacy measures.

Each patient will be assessed by one or more of the following radiologic tests for tumor measurement:

- Computed tomography (CT) scan
- Magnetic resonance imaging (MRI)
- ~~Chest x-ray.~~

...

10.1 General Considerations

...

This is a Phase 1 study with an open-label, dose escalation design. Patients will be enrolled into cohorts sequentially without randomization to dose level. During dose escalation, the total sample size per cohort will be guided by the mTPI method and determined by the occurrences of DLTs (up to 20 patients per cohort before establishing the RP2D and schedule). The total sample size is anticipated to be approximately 50 patients.

10.5 Pharmacokinetic Analyses

Pharmacokinetic analyses will be conducted on patients who have been exposed to study drug and have had samples collected.

Pharmacokinetic parameter estimates for LY3164530 will be calculated by standard noncompartmental methods of analysis.

The primary parameters for analysis will be C_{\max} , $AUC_{0-t_{\text{last}}}$, AUC_{0-T} , and $AUC_{0-\infty}$ of LY3164530. Other noncompartmental parameters, such as $t_{1/2}$, CL, volume of distribution (V), and accumulation ratios may be reported. Additional exploratory analyses will be performed if warranted by the data, and other validated PK software programs may be used if appropriate and approved by Lilly Global PK/PD management. The version of any software used for the analysis will be documented and the program will meet the Lilly requirements of software validation.

Pharmacokinetic parameter estimates will be evaluated to delineate effects of dose proportionality and temporal linearity. Log-transformed C_{\max} and AUC estimates will be assessed to estimate ratios of geometric means and the corresponding 90% confidence intervals (CIs).

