An interim analysis of the LY3164530 PK data was conducted from all of the 15 patients who received at least 1 dose of LY3164530 administered as a 1 or 2-hour infusion once every 2 weeks (Q2W) across the dose range of 300-1250 mg. Dose-dependent increases in the systemic exposure (AUC, C_{max}) of LY3164530 following single and multiple doses were observed. A minor amount of accumulation in serum was observed within Cycle 1 and between Cycles 1 and 2 of treatment after 1000 mg Q2W (mean accumulation ratio of 1.1 within and between cycles). The LY3164530 systemic clearance (CL) decreased by approximately 2-fold on average when the dose was escalated from 600 mg to 1000 mg, indicating the saturation of cell-surface receptors by LY3164530 and a slower non-receptor-mediated clearance predominating at doses >600 mg. While a more rapid receptor-mediated clearance (ie, target mediated drug disposition [TMDD]) predominates at low doses (ie, ≤ 600 mg). In addition, the LY3164530 exposure following 1000 mg Q2W appears to be in an exposure range expected to achieve biological effects based on the nonclinical MKN45 xenograft PK/PD model estimates for the MET and EGFR half maximal effective serum concentrations (EC_{50}) values. The LY3164530 maximum serum concentration (C_{max}) after 1000 mg in Cycles 1 and 2 is greater (mean C_{max} range: 295-394 $\mu\text{g/mL}$) than both the MET EC_{50} (79.5 $\mu\text{g/mL}$; 0.4 μM) and EGFR EC_{50} (7.95 $\mu\text{g/mL}$; 0.04 μM) concentrations. The average LY3164530 serum concentration over the dosing interval ($C_{av,\tau}$) during Cycles 1 and 2 is also greater (mean $C_{av,\tau}$ range: 102-132 $\mu\text{g/mL}$) than the MET EC_{50} and EGFR EC_{50} . However, the minimum serum concentration over the dosing interval ($C_{min,\tau}$) of LY3164530 following 1000 mg in Cycles 1 and 2 (mean $C_{min,\tau}$ range: 19-49 $\mu\text{g/mL}$) is lower than the MET EC_{50} (79.5 $\mu\text{g/mL}$), which is the desired concentration to maintain throughout the dosing interval in order to maximize the biological activity of LY3164530.

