At a dose of 1000 mg, the mean terminal elimination-life ($t_{1/2}$) is approximately 100 hours (approximately 4 days). As a result, the administration of LY3164530 every 2 weeks may not be the optimal schedule of administration in order to achieve a LY3164530 $C_{min,\tau}$ near the MET EC_{50} . Therefore, it is hypothesized that weekly dosing of LY3164530 (ie, Days 1, 8, 15, and 22 of a 28 day cycle) will minimize the fluctuation between the peak (C_{max}) and trough ($C_{min,\tau}$) serum concentrations of LY3164530 leading to a more consistent inhibition of both MET and EGFR over the dosing interval (with minimal impact on the accumulation of LY3164530) and potentially greater pharmacologic activity (PD response). The MTD of LY3164530 when administered on Days 1 and 15 of a 28 day cycle is 1000 mg. As a result, the starting dose for the weekly schedule will be 500 mg. The safety, toxicity, PK, and PD associated with a weekly schedule will be assessed.

6. Investigational Plan

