10.5. Pharmacokinetic Analyses

Pharmacokinetic analyses will be conducted on patients who have been exposed to study drug and have had samples collected.

Pharmacokinetic parameter estimates for LY3164530 will be calculated by standard noncompartmental methods of analysis.

The primary parameters for analysis will be C_{max} , $AUC_{0-t_{last}}$, $AUC_{0-\tau}$, and $AUC_{0-\infty}$ of LY3164530. Other noncompartmental parameters, such as $t_{1/2}$, CL, volume of distribution (V), and accumulation ratios may be reported. Additional exploratory analyses will be performed if warranted by the data, and other validated PK software programs may be used if appropriate and approved by Lilly Global PK/PD management. The version of any software used for the analysis will be documented and the program will meet the Lilly requirements of software validation.

Pharmacokinetic parameter estimates will be evaluated to delineate effects of dose proportionality and temporal linearity. Log-transformed C_{max} and AUC estimates will be assessed to estimate ratios of geometric means and the corresponding 90% confidence intervals (CIs).

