Attachment 3. Protocol JNBA Pharmacokinetic and Pharmacodynamic Sampling Schedule

Pharmacokinetic and Pharmacodynamic Sampling for Schedule 1

Cycle	Day	Collection Time	PK Sampling Time	MET ECD and EGFR ECD ^a	MET and EGFR Ligands ^a	Proteomic Blood Sample ^a
1 and 2	1	Predose	X	X	X	X
	1	Mid-infusion	X			
	1	End of infusion	X	X	X	X
	1	2 hours post end of infusion	X			
	1	4 hours post end of infusion	X			
	1	6 hours post end of infusion (Cycle 1 only)	X			
	2	24 ±4 hours post-end of infusion (Cycle 1 only)	X	X	X	X
	3	Anytime during day (Cycle 1 only)	X			
	8±1	Anytime during day	X			
	15	Predose	X	X	X	X
	15	End of infusion	X	X	X	X
	15	2 hours post end of infusion (Cycle 1 only)	X			
	15	4 hours post end of infusion (Cycle 1 only)	X			
	15	6 hours post end of infusion (Cycle 1 only)	X			
	22±2	Anytime during day (Cycle 1 only)	X			
3-6	1	Predose	X	X	X	X
	1	End of infusion	X			
Follow-ups		Occurs on the day the follow-ups occur.	X	X	X	

Abbreviations: ECD = extracellular domain; EGFR = epidermal growth factor receptor; MET = mesenchymal-epithelial transition factor; PK = pharmacokinetic; V = volume of distribution.

^a Samples are requested to be taken immediately before the dose and immediately after the end of the LY3164530 infusion. Aberrations to specified sampling times will not be considered protocol deviations as long as the samples are taken and the actual sampling time is recorded. It is essential that the actual times of LY3164530 dose and samples are recorded accurately on the appropriate forms.

Pharmacokinetic and Pharmacodynamic Sampling for Schedule 2 Cycle	Day	Collection Time	PK Sampling Time	MET ECD and EGFR ECD ^a	MET and EGFR Ligands ^a	Proteomic Blood Sample ^a
1 and 2	1	Predose	X	X	X	X
	1	Mid-infusion	X			
	1	End of infusion	X	X	X	X
	1	2 hours post end of infusion	X			
	1	4 hours post end of infusion	X			
	1	6 hours post end of infusion	X			
	2	24 ±4 hours post-end of infusion	X	X	X	X
	3	Anytime during day	X			
	8	Predose	X			
	8	End of infusion	X			
	22	Predose	X	X	X	X
	22	End of infusion	X	X	X	X
	22	2 hours post end of infusion (Cycle 1 only)	X			
	22	4 hours post end of infusion (Cycle 1 only)	X			
	22	6 hours post end of infusion (Cycle 1 only)	X			
	23	24 ±4 hours post-end of infusion (Cycle 1 only)	X			
	24	Anytime during day (Cycle 1 only)	X			
3-6	1	Predose	X	X	X	X
	1	End of infusion	X			
Follow-up		Occurs on the day the follow-ups occur.	X	X	X	

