Attachment 3 Protocol JNBA Pharmacokinetic and Pharmacodynamic Sampling Schedule

Pharmacokinetic and Pharmacodynamic Sampling for Schedule 1

Cycle	Day	Collection Time	PK Sampling Time	MET ECD and EGFR ECD ^a	MET and EGFR Ligands ^a	Proteomic Blood Sample ^a
1 and 2	1	Predose	X	X	X	X
	1	Mid-infusion	X			
	1	End of infusion	X	X	X	X
	1	2 hours post end of infusion	X			
	1	4 hours post end of infusion	X			
	1	6 hours post end of infusion (Cycle 1 only)	X			
	2	24 ±4 hours post-end of infusion (Cycle 1 only)	X	X	X	X
	3	Anytime during day (Cycle 1 only)	X			
	8±1	Anytime during day	X			
	15	Predose	X	X	X	X
	15	End of infusion	X	X	X	X
	15	2 hours post end of infusion (Cycle 1 only)	X			
	15	4 hours post end of infusion (Cycle 1 only)	X			
	15	6 hours post end of infusion (Cycle 1 only)	X			
	22±2	Anytime during day (Cycle 1 only)	X			
3-6	1	Predose	X	X	X	X
	1	End of infusion	X			
Follow-ups		Occurs on the day the follow-ups occur.	X	X	X	

Abbreviations: ECD = extracellular domain; EGFR = epidermal growth factor receptor; MET = mesenchymal-epithelial transition factor; PK = pharmacokinetic; V = volume of distribution.

- a Samples are requested to be taken immediately before the dose and immediately after the end of the LY3164530 infusion. Aberrations to specified sampling times will not be considered protocol deviations as long as the samples are taken and the actual sampling time is recorded. It is essential that the actual times of LY3164530 dose and samples are recorded accurately on the appropriate forms.

Pharmacokinetic and Pharmacodynamic Sampling for Schedule 2

Cycle	Day	Collection Time	PK Sampling Time	MET ECD and EGFR ECD^a	MET and EGFR Ligands^a	Proteomic Blood Sample^a
1 and 2	1	Predose	X	X	X	X
	1	Mid-infusion	X			
	1	End of infusion	X	X	X	X
	1	2 hours post end of infusion	X			
	1	4 hours post end of infusion	X			
	1	6 hours post end of infusion	X			
	2	24 ±4 hours post-end of infusion	X	X	X	X
	3	Anytime during day	X			
	8	Predose	X			X
	8	End of infusion (Cycle 1 only)	X			X
	15	Predose (Cycle 1 only)	X	X		X
	15	End of infusion (Cycle 1 only)	X			X
	22	Predose(Cycle 1 only)	X	X	X	X
	22	End of infusion (Cycle 1 only)	X	X	X	X
	22	2 hours post end of infusion (Cycle 1 only)	X			
	22	4 hours post end of infusion (Cycle 1 only)	X			
	22	6 hours post end of infusion (Cycle 1 only)	X			
	23	24 ±4 hours post-end of infusion (Cycle 1 only)	X			
	24	Anytime during day (Cycle 1 only)	X			

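### Schedule 1 AUC ratios between dosing occasions compare unmatched sampling grids and can be biased by sampling alone; state the trapezoidal rule and use common time points

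*Protocol*

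**What the plan says.** Protocol 10.5 lists Cmax and three AUCs, including AUC over the dosing interval (AUC0-τ), as primary PK parameters. The method is given only as "Pharmacokinetic parameter estimates for LY3164530 will be calculated by standard noncompartmental methods of analysis". The section then says "Pharmacokinetic parameter estimates will be evaluated to delineate effects of dose proportionality and temporal linearity", and plans geometric mean ratios with 90% confidence intervals for log-transformed Cmax and AUC. Accumulation is optional ("and accumulation ratios may be reported"), and its basis (AUC, Cmax or trough) is not given.

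SAP 6.12.1 repeats the temporal-linearity and ratio plan, but lists neither AUC0-τ nor accumulation ratios. Neither document names a trapezoidal rule, or says what to do when two occasions are sampled at different times.

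The current Attachment 3 gives these PK profiles (hours are after end of infusion, EOI):

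| Occasion | Samples over the dosing interval |
|---|---|
| Schedule 1, C1D1 | predose, mid-infusion, EOI, 2, 4, 6, 24 h, Day 3, Day 8, Day 15 predose |
| Schedule 1, C1D15 | predose, EOI, 2, 4, 6 h, Day 22, C2D1 predose |
| Schedule 1, C2D1 | predose, mid-infusion, EOI, 2, 4 h, Day 8, Day 15 predose |
| Schedule 2, C1D1 and C2D1 | predose, mid-infusion, EOI, 2, 4, 6, 24 h, Day 3, Day 8 predose |
| Schedule 2, C1D22 | predose, EOI, 2, 4, 6, 24 h, Day 24, C2D1 predose |

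The Schedule 1 row for the day after the first dose is marked "24 ±4 hours post-end of infusion (Cycle 1 only"; the 6 h and Day 3 rows carry the same limit.

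The interim PK paragraphs in Protocol section 5 report, for 1000 mg every two weeks, a "mean accumulation ratio of 1.1 within and between cycles" and a terminal half-life of about 100 h. They say receptor-mediated (saturable) clearance predominates at 600 mg and below. They hypothesise that weekly dosing will flatten peak-trough fluctuation "with minimal impact on the accumulation of LY3164530".

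**The concern.** On Schedule 1, any ratio of a later AUC to the first-dose AUC divides a coarse integral by a fine one. One trapezoid bridges 6 h to about 168 h on C1D15, and 4 h to about 168 h on C2D1, whereas C1D1 has two or three samples inside that gap. The integration errors do not cancel, so the ratio can depart from 1, or from the true accumulation, because of the sampling plan alone. Schedule 2 occasions are matched apart from mid-infusion on Day 22, so they do not share the problem.

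True accumulation with two-weekly dosing is only about 0.1 above 1, so a few per cent of artefact is large relative to what is being measured. The primary objective covers both dose and schedule, and PK is one input to the recommended Phase 2 dose (Protocol 7.2.3).

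**Working it through.** **1. The plan's own figure.** Accumulation R = 1/(1 − exp(−ln2·τ/t½)). With τ = 336 h and t½ = 100 h, exp(−2.329) = 0.0974 and R = 1/0.9026 = 1.108, which agrees with the reported 1.1. Half-lives of 80 and 120 h give 1.06 and 1.17.

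**2. Mono-exponential case.** Inputs: 1-h infusion, t½ 100 h, first-dose EOI concentration scaled to 100, nominal Attachment 3 times counted from the start of infusion, τ = 336 h.

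- C1D1 concentrations at 7, 25, 49, 168 and 336 h: 95.93, 84.67, 71.70, 31.43, 9.81.
- C2D1 concentrations at 5, 168 and 336 h: 107.66, 34.78, 10.86.

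Linear trapezoid pieces:

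- C1D1: 12.5 + 37.5 + 198.6 + 195.9 + 193.2 + 1625.4 + 1876.5 + 6135.8 + 3463.5 ≈ 13,739.
- C2D1: 17.9 + 42.9 + 219.9 + 216.8 + 11,609.3 + 3833.7 ≈ 15,940.

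The C2D1 piece of 11,609 is the single bridge from 5 to 168 h, about (107.66 + 34.78)/2 × 163. The exact area there is 10,514, so it overshoots by 10.4%. Over the same span C1D1 sums to 9831 against an exact 9499, an overshoot of 3.5%.

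- Linear ratio: 15,940/13,739 = 1.160.
- True ratio: 14,464/13,062 = 1.107. Bias: 1.160/1.107 − 1 = +4.8%.
- Linear-up/log-down is exact on this decline and gives 1.107.
- Linear on the common grid: the C1D1 AUC becomes 14,396, and 15,940/14,396 = 1.107.

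For C1D15/C1D1 the linear rule gives 15,756/13,739 = 1.147 against a true 1.098 (+4.5%). On the common grid it gives 15,756/14,353 = 1.098.

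**3. Other curve shapes (assumed parameters), C2D1/C1D1.** The bi-exponential curves are A·exp(−αt) + B·exp(−βt), with the slow half-life 100 h. They were chosen near the protocol's 1000 mg means (Cmax 295–394, Cav 102–132, Cmin 19–49 µg/mL). The saturable curve has one compartment with parallel linear and Michaelis-Menten elimination: V 3.0 L, CL 0.010 L/h, Vm 3.0 mg/h, Km 10 mg/L.

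| Curve | True | Linear, as sampled | Log-down, as sampled | Common grid |
|---|---|---|---|---|
| Bi-exponential, A 88 (20 h), B 257 | 1.100 | 1.236 | 1.147 | 1.091–1.095 |
| Bi-exponential, A 150 (30 h), B 220 | 1.088 | 1.243 | 1.131 | 1.078–1.084 |
| Saturable, 600 mg | 1.000 | 1.075 | 0.799 | 1.000 |
| Saturable, 300 mg | 1.000 | 1.306 | 0.525 | 1.000 |

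A milder assumed saturation at 600 mg gives 1.052 (linear) and 0.949 (log-down) against a true 1.002. A more strongly bi-exponential curve reaches +19% (linear) and +10% (log-down). The 300 mg figures are extremes: concentrations are near zero by Day 15, and handling of values below the assay limit would change them.

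**4. Schedule 2.** The same curves sampled on the Schedule 2 grid give ratios within about 1% of the truth under either rule.

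**5. Cmax and trough.** EOI and predose are sampled on every occasion compared, so ratios built on them do not depend on the missing samples.

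**The case against.** A reader might infer that Schedule 1 accumulation will be overstated, the extra accumulation from weekly dosing understated, and the weekly hypothesis thereby favoured. The documents do not support that.

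- **Direction.** It depends on a trapezoidal rule the plan does not state and on curve shape. Log-down is unbiased for a mono-exponential decline and can be biased downward under the saturable clearance the protocol reports.
- **Observed result.** The interim ratio of 1.1 is what a 100 h half-life predicts. The linear rule would give 1.147 within Cycle 1, which still rounds to 1.1, but 1.160 between cycles, which rounds to 1.2. A bias of about 5% cannot be excluded, given one-decimal rounding, an approximate half-life and an unstated basis. There is no sign of a large one.
- **Use.** No between-schedule contrast of accumulation is specified, accumulation ratios are optional, and the analyses are descriptive. The weekly hypothesis is mainly about peak and trough, which the missing samples do not touch. PK is supporting data for escalation (Protocol 7.2.2.3).
- **Mitigation.** Model-based evaluation (Protocol 10.7) does not need matched grids, and up to five PK samples may be added (8.2.2.1). Both are optional.
- **Schedule 2 match.** For Cycle 2 it rests on Attachment 3 alone, because the treatment schedule in Attachment 1 has no Cycle 2 Day 2 or Day 3 column.

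All of this stands, and it rules out a claim of one-way bias. It does not remove the mismatch. A ratio whose bias may run either way, depending on an unstated choice, is hard to interpret afterwards.

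**Conclusion.** The point holds as a limited one. Schedule 1 between-occasion AUC ratios (temporal linearity, and AUC-based accumulation if reported) rest on unmatched grids and can be biased by sampling alone.

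- **Linear rule:** upward, about +5% for a mono-exponential with a 100 h half-life. The assumed bi-exponential curves give +10% to +19%, and the assumed saturable curves +3% to +31%.
- **Linear-up/log-down:** zero for a mono-exponential, +3% to +10% for the bi-exponentials, and −2% to −48% for the saturable curves.

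Only the mono-exponential figures follow from a half-life stated in the protocol; the others show how far curve shape matters. All assume nominal sampling times and no assay error. Nothing here shows that the reported 1.1 is wrong or that either schedule is favoured. This is a cheap improvement.

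**What to change.** In Protocol 10.5 and SAP 6.12.1, state that AUC is computed by linear-up/log-down trapezoid, and that between-occasion AUC0-τ ratios use, on both occasions, only the nominal time points sampled on both:

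- C2D1 against C1D1: predose, mid-infusion, EOI, 2 h, 4 h, Day 8, Day 15 predose.
- C1D15 against C1D1: predose, EOI, 2, 4, 6 h, about 168 h, 336 h.

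Keep the full-grid AUC for the descriptive C1D1 summary. AUC0-τ must also be added to the SAP's parameter list.

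The cost is a short text addition and one extra AUC run on existing data, with no new visits or samples. The downside is that the ratio ignores the C1D1 24 h and Day 3 samples, and the 6 h sample for C2D1 against C1D1. The Day 8 (±1) and Day 22 (±2) windows leave some mismatch in actual times. A model-based AUC, already allowed by Protocol 10.7, is an acceptable alternative if it is named in advance.
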